2.10.5 Procedure (Active and Sham)

Pregnancy testing

Before the procedure, urine pregnancy tests are required for all women of childbearing potential. In the case of pregnancy, use medical judgement to select appropriate procedural anesthesia medications (eg, low doses of epinephrine and lidocaine) that are safe for use during pregnancy.

Procedure anesthesia

The local anesthesia regimen for the procedure for both active and sham treatments will be performed according to the physician's usual practice. Information regarding the anesthesia regimen will be documented in the study records.

Study procedure

Below is a high-level description of the procedure for both the active and sham procedures. Detailed instructions on the preparation, usage, and storage of the ClariFix device is available in the instructions for use (packaged with the device). To maintain the participant blind during the procedure, the sham devices will be identical to the active devices except the cryogen cannister will not be inserted into the device.

- 1) Review and update concomitant medications.
- 2) Perform quantitative endoscopic rhinoscopy before administration of nasal decongestant to evaluate nasal congestion.
- 3) Administer decongestant. If the participant is a woman of childbearing potential, use medical judgement to select a decongestant (eg, oxymetazoline) that is safe to use during pregnancy.
- 4) Perform quantitative endoscopic rhinoscopy to assess degree/extent of rhinorrhea and postdecongestant nasal congestion, and plan target treatment placement at the middle meatus.
- 5) Administer local anesthesia to both sides of the nasal cavity.
- 6) Have the participant put on the blindfold.
- 7) Prepare the ClariFix device according to the IFU (for sham treatment, do not insert the cryogen cannister).
- 8) Place the cryoprobe in firm contact with the targeted middle meatus tissue under visual guidance.

- 9) For active treatment: initiate the flow of cryogen for a total of 30 seconds and, using endoscopic visualization, ensure the cryoprobe is functioning.

 For sham treatment: turn on the device and leave the cryoprobe in contact with tissue for the 30 seconds, tissue will not freeze with the sham treatment. Use a separate device held near the participant to provide the sound of gas release from the cannister.

 For both treatments, during this time, instruct the participant breathe in and out through their mouth.
- 10) After the treatment (active or sham) wait at least 60 seconds before removing the cryoprobe to allow the cryoprobe to release from the target tissue (active). **During this time, instruct the participant to breathe in through their mouth and out through their nose.**
- 11) Remove the device from the target tissue.
- 12) At the physician's discretion, steps 8 through 11 above may be repeated for a second treatment of up to 30 seconds on the same side.
- 13) Repeat steps 8 to 12 above for treatment on the contralateral side.

The following data will be collected during the study procedure and documented in the appropriate study records:

- Type of anesthesia, including method of administration, location, and dosage
- Individual freeze (or sham) cycle
- Procedure durations (including time roomed, anesthesia start, procedure start, procedure stop, leaves procedure room/treatment chair, discharge)
- Adverse events
- Active or sham treatment
- Device malfunctions

Postprocedure care

Participant will be monitored at the clinic for a minimum of 30 minutes after the procedure. During this time, have the participant complete the blinding questionnaire (for initial randomized treatment only – active or control).

During the postprocedure waiting period, participants will be asked to rate their postprocedure pain/discomfort on a scale of 0 (no pain/discomfort) to 10 (severe pain/discomfort). Any report of severe pain/discomfort (≥7) during the postprocedure waiting period shall be reported as an adverse event. Anesthesia (eg, lidocaine, marcaine) may be injected at the treatment site to alleviate or minimize participant pain.

Postprocedure nasal saline rinses or sprays may be prescribed, as needed, or in accordance with the physician's standard practice.

Concomitant procedures

Concomitant procedures are not allowed in this study. No additional sinonasal procedures should be scheduled within 3 months after the index procedure.

At the physician's discretion, after the 90-day postprocedure visit, ClariFix retreatment or other surgical interventions for rhinitis may be performed for participants who experience continuing or recurrent symptoms. Such treatments will be documented in the study records. The participants will continue to be followed according to their initial follow-up schedule.

2.10.6 30-Day and 90-day follow-up visits

All randomized and treated participants will attend the following postprocedure study visits (window):

- 30-Day in-office visit (±7 days)
- 90-Day in-office visit (±14 days); all participants will be unblinded to treatment assignment at this visit

The following assessments are required at these follow-up visits (also see **Table 2**):

- 1. Patient-reported questionnaires: rTNSS, RQLQ(S), EQ-5D-5L, NOSE, and satisfaction
- 2. Review and update concomitant medications
- 3. Review and update adverse events
- 4. Perform quantitative endoscopic rhinoscopy before administration of nasal decongestant to evaluate nasal congestion
- 5. Administer decongestant and perform quantitative endoscopic rhinoscopy to evaluate treatment site, and assess degree/extent of rhinorrhea and postdecongestant nasal congestion. If the participant is a woman of childbearing potential, use medical judgement to select a decongestant (eg, oxymetazoline) that is safe to use during pregnancy.
- 6. Blinding questionnaire (only for initial randomized treatment active or control)

Control participants who elect to undergo crossover to active treatment after their 90-day visit will repeat these visits after the active treatment procedure. All activities for these visits are repeated and documented except for the blinding questionnaire, which is no longer applicable.

2.10.7 180-Day, 270-day, and 365-day follow-up visits

All participants who receive active treatment (as randomized or crossover participants) will continue with the following long-term visits (window):

- 180-Day visit (±21 days)
- 270-Day visit (±21 days)
- 365-Day visit (±21 days)

The following assessments are required at these long-term follow-up visits (also see **Table 2**):

- 1. Patient-reported questionnaires: rTNSS, RQLQ(S), EQ-5D-5L, NOSE, and satisfaction
- 2. Review and update concomitant medications
- 3. Review and update adverse events
- 4. Perform quantitative endoscopic rhinoscopy before administration of nasal decongestant to evaluate nasal congestion

5. Administer decongestant and perform quantitative endoscopic rhinoscopy to evaluate treatment site, and assess degree/extent of rhinorrhea and postdecongestant nasal congestion. If the participant is a woman of childbearing potential, use medical judgement to select a decongestant (eg, oxymetazoline) that is safe to use during pregnancy.

The study is complete for each participant upon completion of their 365-day follow-up.

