2.10.4 Randomization and blinding

Randomization assignments will be generated by in independent statistician using variable block size distribution by site with a 1:1 allocation to active or sham treatment. Randomization will also be stratified by allergy subgroup (allergic, nonallergic). The randomization schedule will be entered into the Medrio electronic data collection (EDC) randomization module. Randomization will occur on the day of the procedure and after all baseline data have been collected and eligibility has been confirmed. All randomized and treated participants will be considered enrolled. Confirmation of randomization assignment from EDC will be printed and filed in the study record.

This is a single-blind study; participants will be blinded to the randomized assignment. To facilitate blinding, control participants will undergo a sham procedure using the ClariFix device without a cryogen cannister. To support blinding, participants will wear blindfolds during the procedure to limit any visual clues that may suggest the treatment assignment. A separate device with a canister held near the participant will be used to provide the sound of the gas release from the cannister. A standardized script for the physician/staff will be used during the procedure to assure blinding. Additionally, local anesthesia regimes will be the same for both treatment groups within each investigational center.

Participants will complete a blinding questionnaire at completion of the procedure and at the 30-day and 90-day follow-up visits to assess the adequacy of the blinding procedures. Upon

completion of their 90-day visit, each participant will be unblinded. Sham control participants will be offered the opportunity to receive active treatment if they wish and still meet eligibility criteria.

Before the 90-day visit, unblinding of participants will only occur when medically necessary. In the event of a device-or procedure-related SAE, the sponsor may authorize the site to unblind the participant in order to adequately assess the event.

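### Step 12 lets an operator who knows the arm choose the number of treatment cycles, and the protocol text has no rule to keep sham and active cycle numbers comparable

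*Combined protocol and SAP*

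**What the plan says.** Section 2.10.4 blinds the participant only: "This is a single-blind study; participants will be blinded to the randomized assignment". On timing it says "Randomization will occur on the day of the procedure and after all baseline data have been collected and eligibility has been confirmed". It does not say where the assignment is opened relative to the numbered steps of Section 2.10.5.

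Within Section 2.10.5 the steps that matter are these:

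- Step 4 plans where the probe will be placed. It does not mention the number of cycles.
- Step 7 makes the arm known to the operator: "Prepare the ClariFix device according to the IFU (for sham treatment, do not insert the cryogen cannister".
- Step 9 gives each arm a first cycle of 30 seconds. For the control arm, "For sham treatment: turn on the device and leave the cryoprobe in contact with tissue for the 30 seconds", and "tissue will not freeze with the sham treatment".
- Step 10 requires a wait of at least 60 seconds before the probe is removed, in both arms.
- Step 12 says that, at the physician's discretion, "steps 8 through 11 above may be repeated for a second treatment of up to 30 seconds on the same side".
- Step 13 extends this to the other side: "Repeat steps 8 to 12 above for treatment on the contralateral side".

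The stated protections are a blindfold, a second device that makes the gas sound, the same local anesthesia in both arms within a center, a blinding questionnaire, and a script: "A standardized script for the physician/staff will be used during the procedure to assure blinding". The script's content is not given. Section 2.10.5 also calls its steps a high-level description and refers to the instructions for use for detail. Each freeze or sham cycle, the procedure times and the arm are recorded.

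**The concern.** A sham controls for the non-specific effects of a procedure only if both arms go through a similar procedure. Here the number of probe placements, gas sounds and waits can vary from participant to participant, and the person who sets that number knows the arm. The text gives no criterion for repeating, does not ask for the decision before the assignment is known, and does not ask for sham to match active.

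An operator watching tissue freeze might see a reason to repeat. An operator watching a sham has no freeze to judge. The documents state no reason for repeating, so this is a plausible route to imbalance and not one that the protocol describes.

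At stake is the interpretation of the primary comparison. A responder is defined by the rTNSS, which the participant reports (Section 2.11.1). If sham procedures were on average shorter or had fewer placements, part of any difference could reflect procedural expectation and not the cryogen.

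**Working it through.** **1. The plan's own figure.** Inputs from Section 2.6: 73.5% active, 45% sham, one-sided 2.5%, 90% power, 1:1. With pooled variance and no continuity correction, the mean proportion is (0.735 + 0.45)/2 = 0.5925 and

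n per arm = [1.960 × √(2 × 0.5925 × 0.4075) + 1.2816 × √(0.735 × 0.265 + 0.45 × 0.55)]² / 0.285² = 60.4, rounded up to 61.

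This gives 122 in total, as stated. The point made here changes no stated figure.

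**2. Does the operator know the arm before step 12?** Yes. Step 7 differs by arm before the first probe contact, and step 9 differs by arm under endoscopic view. Step 12 follows both.

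**3. Range of exposure.** With one or two cycles on each of two sides, a participant receives 2 to 4 cycles. All times below are minima, because the wait is at least 60 s.

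- First cycle per side: 30 + 60 = 90 s. Both sides: 2 × 90 = 180 s.
- Second cycle per side: s + 60, where s is above 0 and at most 30 s. This is just over 60 s, up to 90 s.
- Two cycles on both sides: 180 + 2 × (just over 60 to 90) = just over 300 s to 360 s.

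**4. Average exposure in an arm.** If a share f of sides receives a second cycle, minimum mean probe time is 180 + f × 2 × (s + 60), which runs from about 180 + 120f to 180 + 180f. The documents give no value of f, so these are assumed:

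| f | Minimum mean probe time |
|---|---|
| 0 | 180 s |
| 0.2 | about 204 to 216 s |
| 0.3 | about 216 to 234 s |
| 0.5 | about 240 to 270 s |
| 0.8 | about 276 to 324 s |

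If f and s are the same in both arms there is no difference. With 0.8 in active and 0.2 in sham the gap is about 72 s (276 − 204) to 108 s (324 − 216). With 0.5 and 0 it is about 60 to 90 s.

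**5. Sensitivity of the primary test to a shift of any origin.** The shifts are assumptions, not estimates of what step 12 would cause. At 61 per arm with no true effect and 45% response, exact enumeration of the one-sided pooled Z-test rejects 2.8% of the time. If the active arm's response is raised by 2.5, 5 or 10 points through expectation alone, it rejects 5.1%, 8.8% or 21.2% of the time. In the other direction, if sham response were 50% or 55% with active at 73.5%, approximate power falls from 90.3% to 76.8% or 57.0%.

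**The case against.** The strongest reply is that imbalance is possible but not shown. Section 2.10.5 covers both arms, and step 12 repeats steps that include the sham branch and its sound device, so a second sham cycle is provided for. The script and the instructions for use are not in the documents, and either could contain a cycle rule. The protocol says that the sham devices are identical apart from the cannister; it does not promise equal numbers of cycles. Each cycle and the procedure times are already recorded, and the questionnaire asks participants which arm they believe they had and why.

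All of this stands, and it limits the point to a gap in the protocol text. It does not close the gap. Providing for a second sham cycle does not make its frequency match. Recording and the questionnaire can reveal a problem but do not prevent it, and Section 2.7 specifies no comparison of cycles or duration by arm. The questionnaire asks about belief in assignment; it does not measure unequal procedural intensity.

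A reader might go further and infer that step 12 unblinds participants. The documents do not support that. Participants are blindfolded, have one randomized procedure and no comparator, and nothing says they are told how many cycles to expect.

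**Conclusion.** The point holds as a design gap. An operator who knows the arm decides on a second cycle per side, and the protocol text has no rule that keeps the arms comparable. Minimum probe time can range from 180 s to between just over 300 s and 360 s, so up to a doubling between participants is allowed.

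A reader might also infer that the result will be biased toward the device by some number of percentage points. That cannot be derived. The documents give neither how often second cycles occur in either arm nor how expectation affects the rTNSS, and more cycles in the active arm is an inference. The false-positive and power figures show only that a modest shift would matter if there were one.

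The conclusion assumes that no arm-independent cycle rule exists in the script or the instructions for use. If one does, the remaining issue is a missing cross-reference. This is an inexpensive improvement, not a defect that invalidates the design.

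**What to change.** - At step 4, have the physician record the intended number of cycles per side before the assignment is opened in the EDC, and state that order in Sections 2.10.4 and 2.10.5. Randomization already takes place on the procedure day, so this is feasible.
- Have sham participants follow the recorded plan.
- Leave clinical discretion in the active arm unchanged, and record any departure from the plan with its reason.
- Report planned and delivered cycles and procedure duration by arm, beside the blinding questionnaire results. Delivered cycles and times are already collected.
- If the script or the instructions for use already contain an arm-independent cycle rule, cite it in step 12.

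None of this sets how many cycles are given or for how long; the sponsor decides both.

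The cost is a wording change, one eCRF field for the plan with space for departures, and longer probe contact for some sham participants. The remedy is partial. An active-arm decision made after seeing the freeze can still depart from the plan, so imbalance from that source is measured and not removed.

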2.9 Concomitant medications

Concomitant medications that should be documented at screening and throughout the study include the following:

- Medications taken for rhinitis, allergies, asthma, sinusitis, migraines, and GERD (or any other ENT, head and neck, respiratory, and/or airway related conditions or systems), including saline.
- Medications administered to treat a study-related adverse event.

Additionally, any medication, as deemed by the investigator, to present a potential safety risk at the time of the procedure (eg, beta-blockers) should be noted as a concomitant medication.

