2.9.1 Prohibited medications

Any participants taking nasal anticholinergic sprays (eg, IB) will be instructed at screening to discontinue use at least 14 days before the baseline visit and through the 90-day follow-up visit.

Participants will also be instructed not to change their baseline concomitant medications (start/stop or change of dose) before the 90-day study follow-up, unless required to treat an adverse event.

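### Postprocedure saline is left to a physician who knows the arm, conflicts with the no-change rule in 2.9.1, and has no equal-arms statement; unequal use could bias the 90-day responder comparison in either direction

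*Combined protocol and SAP*

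**What the plan says.** Four parts of the protocol bear on saline.

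- **Section 2.9** lists what must be documented at screening and throughout the study. The first item covers medications for rhinitis and related conditions: "or any other ENT, head and neck, respiratory, and/or airway related conditions or systems), including saline".
- **Section 2.9.1** sets the rule up to the primary endpoint: "Participants will also be instructed not to change their baseline concomitant medications (start/stop or change of dose) before the 90-day study follow-up". Its only exception is "unless required to treat an adverse event".
- **Section 2.10.5**, under postprocedure care, says: "Postprocedure nasal saline rinses or sprays may be prescribed, as needed", with the physician's standard practice given as the alternative basis. It gives no duration, does not mention the arms and does not refer back to 2.9.1.
- **Section 2.10.4** describes who is blinded: "This is a single-blind study; participants will be blinded to the randomized assignment". It also equalizes one other element of care: "local anesthesia regimes will be the same for both treatment groups within each investigational center".

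The operator necessarily knows the assignment, because step 7 of the procedure in 2.10.5 leaves the cryogen cannister out for sham. The primary endpoint (2.3.1, 2.11.1) is a 30% or greater reduction at 90 days in the rTNSS, a patient-reported sum of four nasal symptoms. Section 2.7 plans no summary, adjustment or sensitivity analysis for concomitant medication.

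**The concern.** There are two linked problems.

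The first is an inconsistency. Routine saline begun after the procedure, with no adverse event, is allowed by 2.10.5 but is a medication start under 2.9.1. Sites may resolve this differently, and deviations would then be counted differently from site to site.

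The second is a gap in the design. An as-needed co-intervention is in the hands of someone who knows the arm, the outcome is the participant's own rating of nasal symptoms, and nothing requires the same practice in both arms. The protocol does guard against this for anesthesia, which 2.10.5 also leaves to the physician's usual practice but 2.10.4 equalizes within each center. The standardized script in 2.10.4 covers the procedure, not aftercare.

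If saline affects the symptoms that the rTNSS scores and its use differs by arm, part of the observed 90-day difference would reflect saline and not cryotherapy.

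**Working it through.** **1. The plan's own figure.** Inputs from section 2.6: active 73.5%, sham 45%, one-sided alpha 0.025, power 90%, 1:1 allocation. With pooled variance and no continuity correction, the mean rate is (0.735 + 0.45)/2 = 0.5925, and

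n per arm = [1.96 × √(2 × 0.5925 × 0.4075) + 1.2816 × √(0.735 × 0.265 + 0.45 × 0.55)]² / 0.285² = 60.4, rounded up to 61.

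This reproduces the stated 122 in total. Power at 61 per arm is 90.3%.

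**2. The texts side by side.**

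| Situation before day 90 | Under 2.9.1 | Under 2.10.5 |
|---|---|---|
| Saline to treat an adverse event | Permitted by the exception | Permitted |
| Routine saline, no adverse event | A medication start, not excepted | Permitted |
| Same practice in both arms | Not addressed | Not addressed |

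The conflict is confined to the second row. The missing equal-arms statement is the third.

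**3. Size if the active arm uses more.** The documents give neither saline usage nor a saline effect, so both are assumptions. Suppose the device is inert and both arms would respond at 45% without saline, leaving 55% non-responders. Let 20% of sham participants use saline, let the active arm use more, and let saline turn a fraction g of would-be non-responders among users into responders. Then

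shift = (usage gap) × g × 0.55.

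For example, 0.40 × 0.20 × 0.55 = 4.4 points, with sham at 0.45 + 0.20 × 0.20 × 0.55 = 47.2% and active at 51.6%. The rejection rate is computed exactly from two binomials, using the pooled Z-test at 1.96 and 61 per arm.

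| Usage, active vs sham | g = 5% | g = 10% | g = 20% |
|---|---|---|---|
| 30% vs 20% | 0.3 points; 3.0% | 0.6 points; 3.2% | 1.1 points; 3.7% |
| 40% vs 20% | 0.6 points; 3.2% | 1.1 points; 3.7% | 2.2 points; 4.8% |
| 60% vs 20% | 1.1 points; 3.7% | 2.2 points; 4.8% | 4.4 points; 7.8% |

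Each cell gives the shift and the one-sided type I error. The right comparator is 2.8%, which is the same exact calculation with no saline effect. It is not the nominal 2.5%, because the discrete test slightly exceeds its nominal level here.

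**4. Size if the sham arm uses more.** Hold the active rate at the planned 73.5% and raise the sham rate by the shift. By the normal approximation, power falls from 90.3% to 89.3% for a 0.5-point shift, 85.8% for 2 points and 80.1% for 4 points.

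**5. Equal use.** If usage and effect are the same in both arms and the device is inert, the shift is zero.

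**The case against.** The best case for leaving the text alone has five parts.

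- **The most obvious source of unequal use is already permitted.** Section 3.2 lists crusting, sloughing and dry nose as potential adverse events of the cold application, so saline for them may fall under the exception in 2.9.1. This stands. It would be wrong to infer that all postprocedure saline breaches 2.9.1; the conflict concerns routine use.
- **Standard practice may make use equal.** It may, but as-needed prescribing is offered as a separate alternative, and nothing requires uniformity under either.
- **The direction is unknown.** This stands. A reader might infer that the bias must favor the device, because the freeze gives reasons to rinse. The documents do not settle it: saline could equally go to sham participants whose symptoms persist.
- **Saline as a cue to assignment is speculative.** This stands. A participant sees only their own prescription, and nothing says that saline will be presented as linked to the arm. The blinding questionnaire (2.11.3) asks for the believed arm and the reasons, so such a cue could come to light.
- **Use is recorded.** Concomitant medications are reviewed at every visit (Table 2), so an imbalance could be described. But section 2.7 plans no such description, and recording does not prevent the imbalance.

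**Conclusion.** The point holds as a cheap improvement, not as a demonstrated bias. Two facts need no assumption: 2.9.1 and 2.10.5 disagree on routine saline before day 90, and a physician who knows the arm may prescribe it with no equal-arms statement.

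The size rests wholly on assumed usage and effect. Over the range examined the shift is about 0.3 to 4.4 points, and with greater active-arm use the type I error is about 3.0% to 7.8% against 2.8%. The top figure needs a 40-point usage gap sustained to day 90 together with 20% conversion. With a 20-point gap the range is 3.2% to 4.8%. Even 4.4 points is modest beside the planned difference of 28.5 points (73.5% minus 45%). A reader might take 7.8% as the trial's actual error rate; the documents support no single figure and no fixed direction.

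**What to change.** Three changes:

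1. Reconcile 2.9.1 with 2.10.5, so that it is clear whether routine postprocedure saline before day 90 is permitted or is a deviation. Which it should be is for the sponsor and centers.
2. State that whatever routine saline practice a center uses applies equally to both arms within that center, in parallel with the anesthesia sentence in 2.10.4. The practice and its duration stay with the sponsor and centers, and treatment of adverse events is unaffected.
3. Prespecify a table of saline use by arm at 30 and 90 days. This also covers adverse-event use, which the second change does not equalize.

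The cost is a few sentences in the protocol, a line in site training and one table from data already collected. The small downside is less physician discretion over routine aftercare before day 90. The sample size does not change.
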